## 8.2 Treatments administered

In the MP (Cycle 1) subjects will be randomized to one of three treatment groups  
CCI

- In Group U, subjects will receive 20 U NT 201 in the GFL area, 20 U NT 201 in the HFL area, and 24 U NT 201 in the LCL area (12 U per side).
- In Group L, subjects will receive placebo in the GFL area, placebo in the HFL area, and 24 U NT 201 in the LCL area, 12 U per side.
- In Group P, all three areas will be treated with placebo.

In the OLEX period (Cycles 2 and 3), all subjects will receive NT 201 in all three areas  
CCI

Injections will be administered as described in Section 8.1.1.2.

CCI

In case of a public health emergency treatments may be halted or postponed.

#### **8.2.1     *Methods of assigning subjects to treatment groups***

At baseline visit V2, subjects will be randomized 2:1:1 to one of the three treatment groups (Groups U, L, or P). Randomization will be done by using an IWRS. Randomization numbers and date of randomization will be recorded in the eCRF.

Randomization will be stratified by investigational site and will be in blocks of appropriate size. This will ensure an approximately equal ratio of treatment groups between sites. The block size will not be disclosed to investigators until the study is unblinded.

No other criteria for stratification of randomization will be applied.

If subjects are discontinued from the study during the MP, no replacement of subjects is planned.

In the MP, for each visit, the system will assign two medication boxes. The medication numbers are scrambled (they will not be in numerical order). Each site will receive scrambled medication numbers per delivery for the MP.

### 8.2.2 Selection of doses in the study

The choice of the doses per treatment area used in this study are justified by experience from prior studies performed with NT 201 CC1  
CC1

CCI

as

CCI

A placebo-controlled study with total doses of 64 U of BoNT-A injected in a comparable manner as planned in this study showed that this dose is safe and effective for the treatment of UFL [De Boulle 2018].

The doses chosen in this study are also in accordance with the treatment doses recommended in the labeling for CCI

CCI

CCI

### 8.2.3 Selection and timing of doses for each subject

[figure not shown]
After a 120 day observation period following injections in cycles 1 and 2, eligible subjects will receive NT 201 reinjection **CC1** at the next cycle baseline visit (V8 for Cycle 2 and V13 for Cycle 3) according to the instructions detailed in **Section 8.1.1.2** and the injection scheme shown in **CC1**. The end-of-Cycle 1 visit V7 and the Cycle 2 baseline visit V8, as well as the end-of-Cycle 2 visit V12 and the Cycle 3 baseline visit V13 should be on the same day if eligibility criteria are fulfilled at V7 and V12, respectively.

CCI

Confidential

CCI

CCI

#### **8.2.4      *Duration of treatment per subject***

Subjects will receive IP at up to three injection visits. The overall study duration for each subject will be approximately 360 days plus the individual duration of screening until baseline (up to 14 days) plus a maximum of 30 days after Cycle 1 and Cycle 2, respectively, for eligibility reassessment as applicable.

In case of a public health emergency the study might be halted, recruitment interrupted and/or study processes and flow might be modified with impact to the study duration/visit schedule depending on the current study status. This might include, but is not limited to, extending study visit windows, performing study visits by phone or video, and/or performing efficacy assessments remotely.

#### **8.2.5      *Treatment compliance***

[figure not shown]
The IP(s) will be administered to the three facial areas by intramuscular injection performed by the investigator during the subject's visits at the site at study baseline (V2) and at cycle baselines in the OLEX period (V8 for Cycle 2 and V13 for Cycle 3). Thus, full treatment compliance is assured for each individual subject.

#### **8.2.6      *Treatment of overdose***

An overdose is defined as any deviation from the specified dose in the protocol (doses that are higher than recommended). Any overdose must be recorded in the IP section, the AE section of the eCRF, and the source documents. Any case of overdose leading to serious adverse events (SAEs) or AEs of special interests (AESI) must be reported to the CRO in an expedited manner using the appropriate reporting form ([Section 10.1](#)).

[figure not shown]
As treatment with IP is performed exclusively in a clinical setting under the supervision of trained medical personnel, the risk of overdose in this study is estimated to be very low. For the IP used in this study, no antidote has been identified to date, and there is no known therapy recommended for an overdose.

CCI

Confidential

CCI

There is no significant information regarding overdose from clinical studies in adults with GFL. In the event of an overdose, the investigator or treating physician is advised to use best clinical judgement and should closely monitor the subject for any AE and SAE and document the quantity of the excess dose. Excessive doses of NT 201 may be expected to produce neuromuscular weakness with a variety of symptoms.

Signs include acute symmetric, descending flaccid paralysis with prominent bulbar palsies such as diplopia, dysphonia, and dysphagia, which would typically occur 12 to 72 hours after exposure [[Armon 2001](#)]. Furthermore, signs and symptoms of overdose can result in ptosis, generalized muscle weakness, and paralysis of respiratory muscle leading to aspiration pneumonia. Clinical cases of iatrogenic botulism after BoNT injection were reported for four adult patients whose clinical signs were consistent with those of naturally occurring botulism [[Chertow 2006](#)].

Symptoms of overdose are not immediately apparent following injection. By the time symptoms of intoxication are observed, treatment with antitoxin will no longer be effective because the neurotoxin has already irreversibly blocked the transmitter release. Compounds releasing acetylcholine (e.g., physostigmine, guanidine, 3,4-diaminopyridine) might be helpful. However, there is no experience with a specific antidote to BoNT including NT 201 in the clinical management of overdose. A published case report describes the successful treatment of dysphagia with intranasal neostigmine [[Marchini 1997](#)].

Subjects should be advised to seek immediate medical care if symptoms such as swallowing difficulties, speech or breathing problems occur. Subjects will receive a subject card with contact information in case of emergency ([Section 3.3.3](#)) if additional information on the scope of the study should be required.

Should accidental injection or oral ingestion occur, the subject should be medically supervised for several weeks for signs and symptoms of excessive muscle weakness or paralysis. Symptomatic treatment may be necessary. Respiratory support may be required where excessive doses cause paralysis of the respiratory muscles. Antitoxin would not reverse any BoNT-induced effects already apparent by the time of antitoxin administration.

### 8.3 Previous and concomitant therapies

Before enrollment, the subject's medical history should include a detailed list of all medications (including rescue medication) that the subject was taking for a period of at least 30 days and for a period of 12 months for non-drug therapies previous to screening. The record should include the drug name (trade or generic), route of administration (e.g., intravenous, oral), total daily dose/unit (expressed in mg, mL, or IU), indication, the start and stop date (day, month, and year) for each medication. At the end of the study, an additional statement will be entered to indicate whether the intake of the medication is ongoing at the end of the study.

Similar information should be collected and assessed for any non-drug therapies that may have an effect on study results.

In addition, the following previous treatments should be checked and listed before enrollment:

- Previous treatment with BoNT of any serotype at any body region at any time.
- Previous treatment with any facial cosmetic procedure CCI [REDACTED]  
[REDACTED] including also biodegradable filler and insertion of permanent material CCI [REDACTED] in the face at any time.

In general, medications, therapies, and procedures that may violate the in- and exclusion criteria (Section 7.2 and Section 7.3) are not permitted during the study.

The following concomitant medications are not permitted during the study:

- Anticoagulants such as heparin, cumarines, non-vitamin K antagonists, oral anticoagulants like CCI [REDACTED] for prophylactic or therapeutic reasons within 10 days prior to injection to 4 days after injection (aspirin and other platelet-aggregation inhibitors CCI [REDACTED])  
[REDACTED] (exclusion criterion no. 20).
- Aminoglycoside antibiotics, or other agents that might interfere with neuromuscular function such as D-penicillamine, curarine-type muscle relaxants, succinylcholine, or that might interfere with the action of BoNT, such as chloroquine, within 14 days prior to injection and during the entire course of the study) (exclusion criterion no. 25).
- Other agents that might interfere with neuromuscular function, i.e. drugs listed in World Health Organization Anatomical Therapeutic Chemical (WHO-ATC) classification class M03 Agents that might induce the production of antibodies

 As previous treatment with BoNT of any serotype in the facial area within the last 12 months before injection is an exclusion criterion (exclusion criterion no. 1), the exact body area of BoNT injection must be documented.

[figure not shown]
 Subjects with previous treatment with any facial cosmetic procedure or biodegradable filler in the face within the last 12 months before injection are excluded from this study (exclusion criterion no. 2)

 Subjects with any previous insertion of permanent material such as silicone, polyacrylamide etc. in the face including any insertion of threads in the upper face or at cheeks, regardless of the time between previous treatment and this study are excluded from study participation (exclusion criterion no. 5)

against acetylcholine receptors (e.g., D-penicillamine), within 14 days before injection and during the entire course of the study.

- Retinoids (exclusion criterion no. 4)
- BoNT treatment of any serotype for any treatment indication during the entire course of the study.
- Any other investigational drug during the entire course of the study.

CCI

Therapy changes (including changes of regimen) during the study are to be documented in the source documentation and in the eCRF.

#### 8.4 Restrictions during the study

[figure not shown]
Not applicable. For restrictions regarding previous and concomitant therapies, see [Section 8.3](#).

CCI

 Previous treatment within 14 days prior to injection with agents that might interfere with neuromuscular function or with the action of BoNT is an exclusion criterion (exclusion criterion no. 24).

CCI

## 9 STUDY ASSESSMENTS AND VISIT SCHEDULE

### 9.1 Assessments

[figure not shown]
Instructions for use of the clinical outcome assessments at site visits in this study will be described in a respective outcome manual (provided by Merz). All assessments will be performed as scheduled according to the study flow chart provided in **CCI** in **Section 9.2**. An overall description of the study plan is provided in **Section 6.1** and in the flow chart in **Section 6.1.2**.

#### 9.1.1 *Clinical assessments*

##### 9.1.1.1 *Efficacy assessments*

[figure not shown]
Assessments performed by the subject should always be done independently from the investigator and study staff at the beginning of a study visit before any investigator's assessments take place to guarantee independence of self-ratings.

CCI

[figure not shown]
To ensure consistent conditions for all subjects, all make-up and evident jewelry has to be removed from the face prior to any standardized photography, the clinical assessments and self-assessments. The study staff will ensure that the subject and investigator can perform assessments independently at a place with adequate lighting and without disturbance at the beginning of the respective study visit. Furthermore, a mirror will be provided so that subjects can control respectively for their facial appearance.

Entries in the source documents need to be dated and signed by the investigator or by the subject.

[figure not shown]

Confidential

CCI

CCI

[figure not shown]

Confidential

[figure not shown]
CCI

CCI

[figure not shown]
Confidential  
CCI

CCI

[figure not shown]

CCI

Confidential

CCI

CCI

[figure not shown]

#### 9.1.1.2 *General assessments*

General assessments include the following:

- Medical history and concomitant diseases, prior and concomitant medication, prior and concomitant non-drug therapies.

CCI

- Subject disposition.
- Demographic data.
- Body height at V1 (screening) and weight at V1 (screening) and V17 End of Study Visit.

---

Confidential

CCI

At the beginning of the study, the subject's demographic data, relevant medical history, concomitant diseases, all prior medication (within 30 days before screening) and all current and concomitant medications and non-drug treatments planned during the study will be recorded. Previous treatments with any facial cosmetic procedure and **CCI** [REDACTED] must be recorded regardless of time of application. For prohibited prior and concomitant therapies, see [Section 8.3](#). A review of this information will allow the investigator to assess whether the subject should be enrolled. Other data will be collected as required, including information obtained from physical examinations and vital signs. If counseling of subjects is deemed necessary, either before enrollment or during the study, counseling will be made available by the investigator involving other medical specialists, if necessary.

### **9.1.2      *Laboratory evaluations***

#### **9.1.2.1      *Clinical and research laboratory evaluations***

Blood samples for evaluation of clinical biochemistry and hematology will be drawn and pregnancy testing performed as described in the study visit schedules for the MP **CCI** [REDACTED] and OLEX period **CCI** [REDACTED]. The samples for hematology and clinical biochemistry, including serum pregnancy testing, will be analyzed at a central laboratory. Details with regard to the methods of sampling as well as the amount of blood to be taken will be described in the respective laboratory manual. See also [Section 9.1.6](#).

In case of pathological laboratory findings, the investigator will discuss these with the subject, if agreed in the informed consent form.

[figure not shown]
**CCI** [REDACTED]

If laboratory evaluations are missing or are unreliable (e.g. due to failed analysis) a re-test of these parameters has to be performed in the central laboratory. Reliable laboratory results for all required parameters have to be available prior to the subject's baseline visit. The results of the re-test will be entered in the study database.

An additional safety laboratory assessment can be performed in the course of an AE if deemed necessary by the investigator and can be evaluated either in a local or the central laboratory. Results of these additional assessments will not be entered in the study database but can be added to the safety database optionally if values are part of safety reporting.

Confidential  
**CCI** [REDACTED]

CCI

#### **9.1.3      *Pharmacodynamics***

Not applicable for this study.

#### **9.1.4      *Pharmacokinetics***

Not applicable for this study. Currently, there are no tests sensitive enough to measure BoNT in peripheral blood.

#### **9.1.5      *Pharmacogenetics***

Not applicable for this study.

[figure not shown]
---

Confidential  
CCI

#### **9.1.6      *Table of blood volume***

CCI

The blood amount corresponds to routine laboratory practice.

Additional blood sampling may be necessary in case of missing values e.g. due to failed analysis.

#### **9.1.7      *Specimen preparation, handling, storage, and shipping***

Blood samples for clinical chemistry, hematology, and  $\beta$ -HCG will be determined by a central laboratory and will be handled according to the manual of the central laboratory. Blood samples will be stored at the central lab until the end of the study and destroyed after study completion.

### **9.2      Visit schedule**

The MP consists of a screening visit V1, which will be performed between Day -14 and Day -3 prior to randomization at baseline (V2; Day 1).

The purpose of the screening visit is to determine subject eligibility for study participation.

Baseline is defined as Day 1, which is the day of randomization and first administration of the IP.

During the double-blind MP, subjects will receive NT 201 or matching placebo once at baseline and will be followed up during five subsequent control visits (V3 to V7). V7 is also the end-of-Cycle 1 visit.

To capture long-term safety and efficacy data for this indication, eligible subjects of all three randomization groups from the MP (Cycle 1) will continue in Cycle 2, where they will receive treatment with NT 201 for all three facial areas at the Cycle 2 baseline visit V8. The end-of-Cycle 1 visit V7 and the Cycle 2 baseline reinjection visit V8 can be performed on the same day if all required eligibility criteria and none of the exclusion criteria of the OLEX period (Section 7.43) are met at V7. Reassessment for eligibility is possible within 30 days after V7 (Section 8.2.3). After treatment in Cycle 2, subjects will

[figure not shown]
be followed up during four control visits (V9 to V12) for 120 days. Control visit V12 is also the end-of-Cycle 2 visit.

After completion of Cycle 2, eligible subjects will continue in Cycle 3, where they will receive treatment with NT 201 for all three facial areas at the Cycle 3 baseline visit V13. The end-of-Cycle 2 visit V12 and the Cycle 3 baseline reinjection visit V13 can be performed on the same day if all required eligibility criteria and none of the exclusion criteria of the OLEX period (Section 7.43) are met at V12. Reassessment for eligibility is possible within 30 days after V12 (Section 8.2.3). After treatment in Cycle 3, subjects will be followed up during four control visits (V14 to V17) for 120 days. Control visit V17 is also the end-of-Cycle 3 and end-of-study visit.

[figure not shown]
The study activities and visit schedules are shown in **CCI** for the MP and in **CCI** for the OLEX period. The clinical study protocol allows for a window of  $\pm 7$  days in scheduling of study visits for all post-baseline visits, except V3 where only a  $\pm 3$ -day window is allowed. The IP(s) must be injected by the investigator, who is trained and experienced in aesthetic BoNT treatment, at the study site. Following administration of IP(s), subjects will be observed for a minimum of 30 minutes at the site and will be asked by the investigator if any AEs have occurred since administration. Vital signs will be taken at the beginning of each study visit to ensure subject safety.

The last primary outcome visit will occur at Day  $30 \pm 7$  (V4) for each subject. For subjects not fulfilling the reinjection criteria, also not at the reassessment visit, the end-of-study visit will be performed directly and the subject will be discontinued from the study. For all other subjects, the end-of-study visit V17 will occur at Day  $120 \pm 7$  after last administration of the IP in Cycle 3. Unscheduled visits may be required in the case of AEs or premature discontinuation of the study. In this case, the final assessments as described for V17, will be performed as soon as possible. If additional safety follow-up is necessary after this visit, subjects may be contacted by telephone or be assessed in the clinic, depending on the nature of the follow-up required.

**CCI**

CCI

[figure not shown]

Confidential

[figure not shown]
CCI

CCI

CCI

[figure not shown]

Confidential

CCI

CCI

CCI

## 10 SAFETY ASSESSMENTS

Safety assessments include AEs, AESIs, standard clinical biochemistry and hematology, vital signs, physical examination, pregnancy test as described in [Section 12.3.5](#) and according to the visit schedules of the MP CC1 and OLEX period CC1

### 10.1 Definition of an adverse event

An AE is any untoward medical occurrence in a subject administered a pharmaceutical product. An AE does not necessarily have a causal relationship with the treatment. Thus, an AE can be any unfavorable and unintended sign, symptom, or disease (including intercurrent illness); deterioration of a pre-existing illness; accident; any suspected drug reaction; or a clinically relevant change of laboratory values whether or not considered related to the IP(s) or study procedure.

Changes in efficacy endpoints (e.g., subject-reported outcome endpoints (questionnaires and scales) during the course of the study) need not be documented as AEs, because these changes will be recorded as efficacy endpoints. Elective treatments planned before screening and which are documented in the subject's source data are usually not regarded as AEs.

For screening failures AEs are not to be documented in the eCRF. For randomized subjects that experienced AEs during the screening period these have to be entered into the eCRF.

Any untoward medical occurrence that happens between the time when the informed consent form was signed and the first administration of IP(s) is an AE and has to be documented in the subject's file and in the eCRF AE report form. These AEs are called non-TEAEs.

TEAEs are defined as AEs with onset or worsening during or after the first administration of IP(s) up to and including final study visit. In case no final visit is performed, all AEs reported during a time period corresponding to the expected cycle length will be regarded as treatment-emergent.

New AEs reported to the investigator during the observation period after the last administration of IP(s) must be documented, treated, and followed up like all other AEs. Non-serious AEs will not be followed up after the final study visit, which is scheduled  $120 \pm 7$  days after last administration of IP(s).

Pre-existing conditions noted in the medical history and previous to study drug administration should not be reported as an AE, unless the condition worsens or the disease reoccurs during the observation period. To determine whether a condition has worsened, it is compared to the condition of the subject at screening. Abnormal laboratory values obtained during the subject's screening period will only meet AE criteria if newly detected and if considered clinically significant.

Data pertaining to AEs will be collected during each study visit on the basis of the subject's spontaneous report, through investigator inquiry, or discovered in the course of examinations performed during the visit. The investigator will assess and record any AE in detail in the source documentation and on the eCRF AE report form. The following information must be recorded:

- AE diagnosis or main symptom.
- Date of onset.
- Date of worsening (e.g. if an AE turns from mild to moderate, the date has to be given).
- Intensity (see [Section 10.1.1](#)).
- Causal relationship (not related, related).
- Causal relationship to COVID-19 (not related, related)
- Serious (yes or no).
- Outcome ([Section 10.1.4](#)).
- AE leading to discontinuation of the study (yes or no).
- Stop date.

After completion of all scheduled visit assessments, the investigator must document any AEs arising from these assessments.

In case of an SAE or AESI (alert term, as defined in [Section 10.3](#)) the investigator must also complete an SAE report form or AESI report form and report it to the CRO immediately, as described in [Section 10.2](#).

Treatment of overdose with IP(s) is described in [Section 8.2.6](#).

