### 10.3 AESIs / alert terms

AEs occurring after treatment that are thought to possibly indicate toxin spread are defined as AESI. The subject will be actively asked by the investigator at each visit after screening (starting with baseline visit V2) if any of the AESI terms listed in CCI below occurred since the last contact. AESI questioning at V2 will facilitate recording of pre-existing conditions and/or possibly undetected (S)AEs that could confound AESI questioning post injection of IP. The questioning and documentation of answers will be standardized.

AESIs are considered to have a special meaning or importance for a particular drug or class of drugs. They may be non-serious and precursors (prodromes) of more serious medical conditions. Thus, they should be closely monitored and reported to the sponsor within 24 hours.

The site must report all AESIs that occur during the study period, whether considered to be related to IP(s) or not, by telefax or email to the responsible CRO within 24 hours of knowledge of the event. The CRO will transmit these AESIs to Merz Pharmaceuticals GmbH. Each AESI must be reported by the site on the AESI reporting form. Moreover, AESIs are to be documented on the general pages of the AE eCRF as well as in the subject's file. The eCRF pages for medical history/concomitant diseases and for previous/concomitant medication and non-drug treatment are to be faxed/sent along with the AESI reporting form. The AEs in **CCI** [REDACTED] are defined as AESIs for this study.

CCI

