TEAEs of the MP are defined as AEs with onset or worsening on or after date and time of the first administration of IP at V2 and before date and time of administration of IP in V8 (Cycle 2) or up to and including end of study visit (V17) in case of premature discontinuations prior to V8. For subjects who do not receive study treatment during OLEX period all AEs with onset or worsening on or after date and time of the first administration of IP up to and including end of study visit (V17) will be considered as TEAEs of MP. In case no end of study visit (V17) is performed, all AEs with onset or worsening up to and including Day 120 of MP will be regarded as TEAEs of MP.

TEAEs of the total OLEX period are defined as AEs with onset or worsening on or after date and time of the first administration of IP during OLEX period at V8 and up to and including end of study visit (V17). In case no end of study visit (V17) is performed, all AEs with onset or worsening at or after date and time of the first administration of IP during OLEX period at V8 and up to and including Day 120 of last cycle will be regarded as TEAEs of OLEX. TEAEs of Cycle 2 are defined as AEs with onset or worsening on or after date and time of the first administration of IP at V8 and before date and time of administration of IP at V13 (Cycle 3) or up to and including end of study visit (V17) in case of premature discontinuations prior to V13 or in case no study treatment is administered at V13. In case no end of study visit (V17) is performed, all AEs with onset or worsening at or after date and time of the first administration of IP at V8 and up to and including Day 120 of Cycle 2 will be regarded as TEAEs of Cycle 2. TEAEs of Cycle 3 are defined as AEs with onset or worsening on or after date and time of the first administration of IP at V13 and up to and including end of study visit (V17). In case no end of study visit (V17) is performed, all AEs with onset or worsening at or after date and time of the first

administration of IP at V13 and up to and including Day 120 of Cycle 3 will be regarded as TEAEs of Cycle 3.

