For analysis over the total study period, the number of subjects in the SES will serve as the denominator for calculation of incidences. For the analyses by treatment cycle the denominator will be adjusted to all subjects being treated in that treatment cycle. For the analysis over the total OLEX period, the denominator for the incidences will be all subjects being treated at least once in total OLEX period.

If an AE worsens between start and end of this AE it will be considered as new AE starting with the date of worsening. In this case the imputation of end dates within episodes of the same AE will be done by setting the end date/end time to start date/start time of the consecutive worsening record.

For analysis, incompletely recorded or completely missing start of AEs will be estimated according rules laid down in **cci** [REDACTED] End dates will not be imputed. In the AE listing, start date as recorded and as imputed for analysis will be displayed.

Calculation of time to onset/duration of AEs (days):

- Time to onset of an AE is defined as start date of AE - date of first administration of study drug in respective treatment cycle [+ 1 day for TEAEs]
- The duration of an AE will be calculated as stop date - onset date + 1 day.

If a subject has more than one intensity/ causal relationship to treatment/ outcome within a preferred term (PT) only the worst intensity/ causal relationship to treatment/ outcome will be considered for calculation of incidence rates in the frequency tables reporting incidences by intensity/ causal relationship to treatment/ outcome. Incidence of TEAEs related to COVID-19 disease and TEAEs related to COVID-19 vaccination will only be calculated overall. Thereby, TEAEs with missing relationship will be ignored but affected subjects will not be removed from the denominator. Also, for the analysis overall, i.e. for subjects with at least one TEAE, only the worst intensity/ causal relationship to treatment/ outcome category per subject will be counted for calculating incidence rates. The same applies to calculation of overall incidence of TEAEs related to COVID-19 disease and TEAEs related to COVID-19 vaccination.

[figure not shown]
The worst outcome is defined in the following order (worst outcome to best outcome):

- fatal
- unknown
- not recovered/not resolved
- recovering/resolving
- recovered/resolved with sequelae
- recovered/resolved

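### Worsening of a pre-existing condition is judged only against screening, while TEAEs are dated from the injections, so a partly improved condition that worsens again may go unreported

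*Protocol*

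**What the plan says.** Protocol section 10.1 does not treat a pre-existing condition in the medical history as an adverse event "unless the condition worsens or the disease reoccurs during the observation period". The next sentence sets the yardstick: "To determine whether a condition has worsened, it is compared to the condition of the subject at screening". No other reference is given, and nothing limits this one to the main period.

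The same section fixes treatment emergence at the injection: "TEAEs are defined as AEs with onset or worsening during or after the first administration of IP(s) up to and including final study visit". SAP section 6.2 carries this through by cycle. For Cycle 2 the wording, which goes on to name V8, is "TEAEs of Cycle 2 are defined as AEs with onset or worsening on or after date and time of the first administration of IP at". For Cycle 3 the same wording is tied to V13.

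Other clauses bear on the point:

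- The general definition in Protocol 10.1 includes "deterioration of a pre-existing illness" and any suspected drug reaction, without naming a comparator for either.
- Anything untoward between consent and the first injection is an adverse event. Once an event is recorded, the site gives the date of any worsening, and the SAP adds: "If an AE worsens between start and end of this AE it will be considered as new AE starting with the date of worsening".
- Protocol 10.3 has the investigator ask about the adverse events of special interest (AESI) at every visit from V2, and explains that "AESI questioning at V2 will facilitate recording of pre-existing conditions".

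The secondary safety endpoints (Protocol 12.3.5.2, SAP 5.2.2) are the incidences of related TEAEs in the main period and in the open-label extension.

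**The concern.** Two clauses of one section measure worsening from different points. The TEAE definition asks whether something became worse after an injection. The pre-existing-condition clause asks whether it is now worse than at screening. The answers differ when the condition changed between screening and the injection.

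Take a continuing condition that is moderate at V1, mild just before the V2 injection and moderate again a few days later. It has worsened since the injection, which is what a TEAE is meant to capture. It is no worse than at screening, so a site that follows the yardstick has no worsening to report.

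The clause operates when the site decides whether to make a record. If no record is made, the SAP's rules for assigning events to periods have nothing to work on, and no later analysis can restore the event. In the cases worked through below, the error runs in one direction, towards a lower post-injection incidence. Repeat-dose safety is a secondary objective, and the screening reference is oldest in the repeat-dose cycles.

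**Working it through.** There is no sample size, power or alpha figure to reproduce. The check has two parts: which courses of a condition are missed, and how old the screening reference is at each injection.

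**Courses missed under the literal rule.** Grade a condition as absent (0), mild (1), moderate (2) or severe (3). Let s be its grade at screening, b its grade just before the injection and p its grade afterwards. Take s of at least 1 (pre-existing) and p > b (a true post-injection worsening).

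- Pairs with p > b: 6. With three values of s: 3 × 6 = 18 courses.
- The rule makes a course reportable if p > s (worse than screening), or if b = 0 (resolved, then reoccurred).
- b = 0: 3 values of s × 3 values of p = 9 courses, all reportable as reoccurrence.
- b of at least 1: 9 courses. Of these, p > s holds in 3 (s = 1), 2 (s = 2) and 0 (s = 3), so 5 are reportable.
- Not reportable: 18 − 9 − 5 = 4. As (s, b, p) they are moderate–mild–moderate, severe–mild–moderate, severe–mild–severe and severe–moderate–severe.

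These are counts of possible courses, not frequencies. In each of the four, the condition was still present but milder just before the injection.

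**Age of the screening reference.** Inputs: screening 3 to 14 days before V2, a ±7-day window on post-baseline visits, and reassessment up to 30 days after V7 or V12 (all Protocol 9.2); cycles of 120 days (Protocol 6.1). The shortest case has V7 and V8, and V12 and V13, on the same day, as the Protocol allows.

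- V2: 3 to 14 days.
- V8, no windows: 3 + 120 = 123 to 14 + 120 + 30 = 164 days. With windows: 3 + 113 = 116 to 14 + 127 + 30 = 171 days.
- V13, no windows: 3 + 2 × 120 = 243 to 14 + 2 × (120 + 30) = 314 days. With windows: 3 + 2 × 113 = 229 to 14 + 2 × (127 + 30) = 328 days.

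So the yardstick is at most about two weeks old at the first injection, roughly four to six months old at the second and eight to eleven months old at the third.

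**What would be needed for a rate.** The number of lost events depends on how many subjects have a continuing condition, how often it partly improves before an injection, how often it then worsens without exceeding its screening grade, and how often the site makes no record by another route. The documents give none of these.

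**The case against.** A reader might infer that a post-injection worsening back to the screening level is never recorded. The documents do not support that. A condition that resolved and came back is reportable under the reoccurrence clause. The screening yardstick applies only to pre-existing medical-history conditions: events arising after consent are adverse events in their own right, and their later worsening is dated and counted. AESI terms are asked about at each visit from V2.

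The strongest objection concerns the endpoint, which is related TEAEs. A worsening that the investigator thinks may be due to the injection is a suspected drug reaction, which Protocol 10.1 lists as an adverse event without reference to screening. Protocol 10.1.2 also sets a low threshold for relatedness. On that view the events lost are mainly fluctuations unrelated to treatment. This weakens the link to the endpoint but does not remove the conflict. The sentence on pre-existing conditions is the more specific one, the text does not say which clause prevails, and sites could read it differently.

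A reader might also infer a bias in the comparison with placebo, or want a percentage. Neither is supported. The rule is the same in all blinded arms and the main-period reference is recent. A simulated share of lost events would be set by the assumed grade mix and the assumed correlation between the two time points, and over 3 to 14 days that correlation is likely to be high.

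Some material cannot be checked. The visit schedules and the SAP's detailed rules for separating TEAEs from other events are redacted. Rules of that kind work on recorded events, so they could not restore an unrecorded one. Nor do the visible pages show that pre-existing conditions are graded at V2, V8 and V13, so a pre-injection comparator is not entirely free.

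**Conclusion.** The point holds in a limited form. The pre-existing-condition yardstick and the TEAE definition use different reference points, and no visible text reconciles them. Read literally, a continuing medical-history condition that partly improved before an injection and then worsened to no more than its screening level is not reportable as worsened, and may not enter the TEAE tables.

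In the main period the likely effect is a small undercount, equal across arms. This assumes that most conditions change little in two weeks and that blinded sites apply the rule alike. The open-label extension is more exposed: the reference is months old, there is no concurrent control, and the reported figure is an absolute incidence, so equal treatment of former arms gives no protection. The direction is downward and the size is unknown. The correction is worth making because it is cheap and because unrecorded events cannot be recovered. It changes no sample size, error rate or efficacy analysis.

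**What to change.** Bring the yardstick in Protocol 10.1 into line with the TEAE definition. Suggested wording: *After an injection, a pre-existing condition is compared with its last known state before the most recent injection; before the first injection it is compared with its state at screening.* Add that any suspected drug reaction is reported regardless of the state at screening, so that the general definition and the pre-existing-condition clause cannot be read against each other.

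The cost is one replaced sentence, the added statement, a line in site training, and a short note of the status of ongoing conditions at V2, V8 and V13, taken during the existing adverse-event inquiry. Expect a slightly higher adverse-event count. If subjects have already been treated under the present wording, the study report should say which reference applied to which cycles.
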